## 8.5 Treatment of Overdose

For purposes of this study, an overdose will be defined as any dose exceeding the prescribed dose for nemtabrutinib. No specific information is available on the treatment of overdose of nemtabrutinib. In the event of overdose, the participant should be observed closely for signs of toxicity. Appropriate supportive treatment should be provided if clinically indicated. If an AE is associated with an overdose of, nemtabrutinib the AE must be reported as a SAE, even if no other seriousness criteria are met. All reports of overdose associated with an AE must be reported by the investigator within 24 hours to the Sponsor either by electronic media or paper. If a dose of nemtabrutinib meeting the protocol definition of overdose is taken without any associated clinical symptoms or abnormal laboratory results, the overdose is reported as a non-serious ECI, using the terminology "accidental or intentional overdose without adverse effect."

## **8.6 Pharmacokinetics**

To evaluate the pharmacokinetic profile of nemtabrutinib, sample collections for analysis of PK is currently planned as shown in Section 1.3 and in [Table 1](#). Blood samples will be obtained to measure plasma PK of nemtabrutinib.

Sample collection, storage, and shipment instructions for plasma samples will be provided in the Laboratory Manual.

## **8.7 Pharmacodynamics**

Sample collection, storage, and shipment instructions for pharmacodynamic samples will be in the Central Laboratory Manual.

## **8.8 Biomarkers**

To identify novel biomarkers, the following biospecimens to support exploratory analyses of cellular components (eg, protein, RNA, DNA, metabolites) and other circulating molecules will be collected from all participants in this study as specified in the SoA:

- Blood for BTK C481 mutation status. (CLL/SLL participants only)
- Blood for genetic analysis.

Sample collection, storage and shipment instructions for the exploratory biomarker specimens will be provided in the Laboratory Manual.

### **8.8.1 Planned Genetic Analysis Sample Collection**

The planned genetic analysis sample should be drawn for planned analysis of the association between genetic variants in DNA and drug response. This sample will not be collected at the site if there is either a local law or regulation prohibiting collection, or if the IRB/IEC does not approve the collection of the sample for these purposes.

Sample collection, storage, and shipment instructions for planned genetic analysis samples will be provided in the Laboratory Manual.

## **8.9 Future Biomedical Research Sample Collection**

FBR samples will not be collected in this study.

## **8.10 Medical Resource Utilization and Health Economics**

Medical Resource Utilization and Health Economics are not evaluated in this study.

## **8.11 Visit Requirements**

Visit requirements are outlined in Section 1.3. Specific procedure-related details are provided in Section 8.

### **8.11.1 Screening**

Approximately 28 days prior to intervention allocation, potential participants will be evaluated to determine that they fulfill the entry requirements as set forth in Section 5.

Documented informed consent must be provided before performing any protocol-specific procedure. Results of a test performed before the participant signing consent as part of routine clinical management are acceptable in lieu of a screening test if performed within the specified time frame.

Screening procedures are to be completed within 28 days before the first dose of study intervention.

Laboratory tests are to be performed within 7 days prior to the first dose of study intervention. An exception is hepatitis testing, which may be done up to 28 days prior to the first dose of study intervention.

Evaluation of ECOG is to be performed within 7 days prior to the first dose of study intervention.

For women of reproductive potential, a urine or serum pregnancy test will be performed within 24 hours prior to the first dose of study intervention. If urine pregnancy results cannot be confirmed as negative, a serum pregnancy test will be required (performed by the local study site laboratory).

Participants may be rescreened after initially failing to meet the inclusion/exclusion criteria with the agreement of the sponsor. Results from assessments during the initial screening period are acceptable in lieu of a repeat screening test if performed within the specified time frame and the corresponding inclusion/exclusion criteria are met. Participants who are rescreened will retain their original screening number.

### **8.11.2 Treatment Period Visit**

Visit requirements are outlined in the SoA (Section 1.3). Specific procedure-related details are provided in Section 8.1.

Unless otherwise specified, assessments/procedures are to be performed prior to the first dose of study intervention for each cycle, and the window for each visit as defined in the SoA.

In or after cycle 4, participants receiving 45 mg of nemtabrutinib may be escalated to 65 mg if the tolerability is confirmed at 65 mg of nemtabrutinib and at the discretion of the investigator after discussion with the participant, upon the consultation with sponsor. If the escalation is permitted, the higher dose can be utilized from the Day 1 of next cycle based on the approved date. The participants who receive the higher dose of nemtabrutinib should perform site visit / telephone contact after 14 ( $\pm 3$  days) days and 28 ( $\pm 3$  days) days from the first dose of the escalated dose. Refer to Section 1.3 for the detailed schedule.

In or after cycle 28, the participants will visit the site every 3 cycles. Between these 3 cycles, the site visit / telephone contact is required when each cycle (e.g., cycle 29 and cycle 30) will start.

### **8.11.3 Participants Discontinued From Study Intervention but Continuing to be Monitored in the Study**

The Discontinuation Visit should occur at the time study intervention is discontinued for any reason. If the Discontinuation Visit occurs 30 days from the last dose of study intervention, at the time of the mandatory Safety Follow-up Visit, the Discontinuation Visit procedures and any additional Safety Follow-up procedures should be performed. Visit requirements are outlined in Section 1.3. Additional details regarding participant withdrawal and discontinuation are presented in Section 7.

### **8.11.4 Safety Follow-up Visit**

The mandatory Safety Follow-up Visit should be conducted approximately 30 days after the last dose of study intervention or before initiation of a new anticancer treatment, whichever comes first.

All AEs that occur before the Safety Follow-up Visit should be recorded (up to 30 days after the end of treatment).

### **8.11.5 Efficacy Follow-up Visits**

Participants who discontinue study intervention for reasons other than PD should continue with imaging assessments per the protocol-defined schedule until: (1) site assessed initial PD or further confirmed by the investigator, (2) initiation of a new anticancer treatment, (3) death, (4) withdrawal of consent, (5) pregnancy, or (6) study conclusion or early termination, whichever occurs first. All new anticancer therapy initiated after the study intervention discontinuation must be recorded in the CRF. If a participant initiates another anticancer therapy other than the assigned study intervention, the study intervention should be discontinued. If a participant initiates a new anticancer therapy within 30 days after the last dose of the study intervention, the 30-day Safety Follow-up visit should occur before the first dose of the new therapy.

NOTE: Efficacy follow-up assessments should follow calendar days from allocation. If dosing is delayed, efficacy assessments should continue as scheduled.

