Window (days)	-28 to -1	0	0	0	0	±3	±3	±3	±3		+7	±7	±14	
Subsequent antineoplastic therapy status										X	X	X	X	Any change in new treatment will be collected. After approval of Protocol amendment 04, participants in the Survival Follow-up phase will be discontinued from the study and no further visits will be required.
Safety Procedures														
Adverse Event monitoring		X	X	X	X	X	X	X	X	X	X			Report AEs occurring within 30 days after the last dose of study intervention. Report SAEs occurring within 90 days after the last dose of study intervention or 30 days after the last dose of study intervention if the participant initiates new anticancer therapy, whichever comes first.

Study Period	Screening Phase	Treatment Phase								End of Treatment (EOT)	Post-Treatment			Notes: Each cycle consists of 4 weeks (28 calendar days). If dosing is interrupted or delayed see Section 6.1.1 for details.
Treatment Cycle/Day		C1				C2	C3	C4~C27	C28+		Safety Follow-up	Efficacy Follow-up	Survival Follow-up	
		1	8	15	22	1	1	1	1					
Visit Number/Frequency	1	2	3	4	5	6	7	Every cycle	Every 3 cycles	At treatment discontinuation	30 days after post discontinuation	Every 12 weeks	Every 12 weeks	
Window (days)	-28 to -1	0	0	0	0	±3	±3	±3	±3		+7	±7	±14	
														When clinic visits are conducted every 3 cycles, the site will contact the participant every cycle to monitor and record AEs.
Physical Examination	X	X	X	X	X	X	X	X	X	X	X			A complete physical examination will be conducted at screening only. For subsequent cycles, a directed physical examination will be performed.
Hight	X													
Weight	X	X	X	X	X	X	X	X	X	X	X			
Vital Sign (pulse, respiratory rate, blood pressure, temperature), SpO 2 measurement	X	X	X	X	X	X	X	X	X	X	X			The measurement of SpO 2 is performed by the investigator or designee by the standard method in each study site.
ECOG Performance Status	X	X	X	X	X	X	X	X	X	X				Screening assessment to be performed within 7 days prior to the first dose of study intervention.

Study Period	Screening Phase	Treatment Phase								End of Treatment (EOT)	Post-Treatment			Notes: Each cycle consists of 4 weeks (28 calendar days). If dosing is interrupted or delayed see Section 6.1.1 for details.
Treatment Cycle/Day		C1				C2	C3	C4~C27	C28+		Safety Follow-up	Efficacy Follow-up	Survival Follow-up	
		1	8	15	22	1	1	1	1					

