Visit Number/Frequency	1	2	3	4	5	6	7	Every cycle	Every 3 cycles	At treatment discontinuation	30 days after post discontinuation	Every 12 weeks	Every 12 weeks	
Window (days)	-28 to -1	0	0	0	0	±3	±3	±3	±3		+7	±7	±14	
Triplicated 12-lead ECG	X	See Table 1								X				Post Cycle 3, ECG assessment only required where clinically indicated.
DLT evaluation		X	X	X	X									
Laboratory Procedures														
Hematology, Serum Chemistry	X	X	X	X	X	X	X	X	X	X	X			Screening assessment to be performed within 7 days prior to the first dose of study intervention.
Tumor Lysis Syndrome (TLS) Monitoring (High Risk Participants only)		See Table 1												See Section 8.1.10.
Urinalysis	X													Screening samples must be taken within 7 days prior to the first dose of study intervention. Postscreening sample only required if clinically indicated.

Study Period	Screening Phase	Treatment Phase								End of Treatment (EOT)	Post-Treatment			Notes: Each cycle consists of 4 weeks (28 calendar days). If dosing is interrupted or delayed see Section 6.1.1 for details.
Treatment Cycle/Day		C1				C2	C3	C4~C27	C28+		Safety Follow-up	Efficacy Follow-up	Survival Follow-up	
		1	8	15	22	1	1	1	1					
Visit Number/Frequency	1	2	3	4	5	6	7	Every cycle	Every 3 cycles	At treatment discontinuation	30 days after post discontinuation	Every 12 weeks	Every 12 weeks	
Window (days)	-28 to -1	0	0	0	0	±3	±3	±3	±3		+7	±7	±14	
Pregnancy Test (WOCBP only)	X	X				X	X	X	X	X	X			WOCBP require negative test prior to allocation. If more than 24 hours have elapsed prior to first dose of study intervention, another pregnancy test is required prior to starting study intervention. Pregnancy tests should be performed monthly and/or as per local regulations. Home pregnancy tests are acceptable when a scheduled visit does not occur within the month (per local regulation), but the site must make monthly telephone contact with the participant to determine the results of the pregnancy test.

Study Period	Screening Phase	Treatment Phase								End of Treatment (EOT)	Post-Treatment			Notes: Each cycle consists of 4 weeks (28 calendar days). If dosing is interrupted or delayed see Section 6.1.1 for details.
Treatment Cycle/Day		C1				C2	C3	C4~C27	C28+		Safety Follow-up	Efficacy Follow-up	Survival Follow-up	
		1	8	15	22	1	1	1	1					
Visit Number/Frequency	1	2	3	4	5	6	7	Every cycle	Every 3 cycles	At treatment discontinuation	30 days after post discontinuation	Every 12 weeks	Every 12 weeks	

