Window (days)	-28 to -1	0	0	0	0	±3	±3	±3	±3		+7	±7	±14	
β2 Microglobulin	X	X				X	X	X	X					
Serum Immunoglobulin	X	X				X	X	X	X					For IgG, IgA, and IgM
Creatinine clearance	X													
Infection Testing (HCV, HBV, HIV)	X	← Participants with a history of HBV →												Monitoring is required for participants with a history of HBV, if clinically indicated during treatment phase.
Pharmacokinetics/Pharmacodynamics/Biomarkers (Central)														
Blood Samples for PK		See Table 1												
Blood Samples for PD		See Table 1						X*						For C1 to C3: See Table 1 *: Predose Samples will be collected on C4D1, C5D1 and C6D1.

Study Period	Screening Phase	Treatment Phase								End of Treatment (EOT)	Post-Treatment			Notes: Each cycle consists of 4 weeks (28 calendar days). If dosing is interrupted or delayed see Section 6.1.1 for details.
Treatment Cycle/Day		C1				C2	C3	C4~C27	C28+		Safety Follow-up	Efficacy Follow-up	Survival Follow-up	
		1	8	15	22	1	1	1	1					
Visit Number/Frequency	1	2	3	4	5	6	7	Every cycle	Every 3 cycles	At treatment discontinuation	30 days after post discontinuation	Every 12 weeks	Every 12 weeks	
Window (days)	-28 to -1	0	0	0	0	±3	±3	±3	±3		+7	±7	±14	
Blood for BTK C481 mutation analysis (CLL/SLL participants only)		X												Predose sample required.
Blood for Genetic Analysis		X												Predose sample required. See Section 8.8

Abbreviations: BM=bone marrow; BTK=Bruton's tyrosine kinase; CLL=chronic lymphocytic leukemia; CR=complete response; DLT=dose-limiting toxicity; ECG=electrocardiogram; ECOG PS=Eastern Cooperative Oncology Group performance status; EOT=end of treatment; HBV=hepatitis B virus; HCV=hepatitis C virus; HIV=human immunodeficiency virus; ID=identification; Ig=immunoglobulin; LPL=lymphoplasmacytic lymphoma; MRD=minimal residual disease; PB=peripheral blood; PD=pharmacodynamics; PK=pharmacokinetics; q12w=every 12 weeks; SLL=small lymphocytic lymphoma; WM=waldenström's macroglobulinemia; WOCBP=women of childbearing potential.

Table 1 Collection schedule of PK, PD samples, ECG (TriPLICATE) assessments and TLS Monitoring (Cycles 1 to 3)

Study Period	Treatment phase																	Notes: Each cycle consists of 4 weeks (28 calendar days)		
Treatment Cycle/Day	C1D1							C1 D2	C2D1						C2 D2	C3D1				
Visit Number	2							6						7						
Time frame (hours)	Pre do se	Post dose							Pre do se	Post Dose						Pre do se	Post dose			
		1	2	4	6	8	10	24		1	2	4	6	8	10	24		2	4	

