## **8.2 Efficacy Assessments**

Treatment response assessments (including imaging, physical examinations, constitutional symptoms, hematological evaluations, and bone marrow as required) are required every 12 weeks ( $\pm 7$  days) and should follow calendar days from C1D1. The frequency of treatment response assessment can be decreased to every 24 weeks ( $\pm 7$  days) starting the fourth year on study. If dosing is delayed, treatment response assessments should continue as scheduled. For further details refer to the SoA in Section 1.3.

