### **8.2.2.1 Disease Progression Assessment**

#### **8.2.2.1.1 Imaging Assessment**

If an investigator concludes the participant’s disease has progressed, study treatment must be discontinued unless confirmation is required for clinically stable participants. The participant will enter post-treatment follow-up; ie, 30-day Safety Follow-up and Survival Follow-up. For participants who discontinue study intervention, tumor imaging should be performed at the

time of treatment discontinuation ( $\pm 4$ -week window). If previous imaging was obtained within 4 weeks prior to the date of discontinuation, then imaging at treatment discontinuation is not mandatory. For participants who discontinue study intervention due to documented disease progression, this is the final required tumor imaging.

For participants who discontinue study intervention without documented disease progression, every effort should be made to continue monitoring disease status by tumor imaging using the same imaging schedule used while on treatment calculated from the date of Cycle 1 Day 1 until the start of a new anticancer treatment, disease progression, pregnancy, death, withdrawal of consent, or the end of the study, whichever occurs first.

It is at the discretion of the investigator to stop study treatment or to keep a clinically stable participant on study treatment until repeat imaging performed 4 to 6 weeks later confirms progression. Participants that are deemed clinically unstable should not have repeat imaging for confirmation. Clinical stability may be defined as:

- Absence of symptoms and signs indicating clinically significant progression of disease (including worsening of laboratory values).
- No decline in ECOG performance status.
- Absence of rapid progression of disease or progressive tumor at critical anatomical sites requiring urgent medical intervention (eg, cord compression).

If progression is confirmed by subsequent imaging, then the participant will be discontinued from study treatment. If progression is not confirmed, then the participant should resume/continue study treatment provided:

- The Sponsor is consulted and provides approval to continue treatment.
- No other antitumor therapy (eg, chemotherapy, radiation, etc.) has been administered.

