### ***Partial Response with Lymphocytosis (PRL)***

The overall response will be PRL when ALL of the following criteria are met:

- Lymphocyte count is stable or increased from baseline
- All other criteria for PR or better are met.

An increase in blood lymphocyte count by itself does not uniformly indicate an increased tumor burden but may reflect redistribution of leukemia cells from lymphoid tissues to the blood. In such cases, increased lymphocytosis alone is not a sign of treatment failure.

**Progressive Disease (PD)** if any of the parameters in group A or B indicate progression

- Group A:
  - Lymph node response is PD
  - Liver and spleen assessment shows PD
  - Circulating lymphocytes increase  $\geq 50\%$  from nadir (unless PRL, as above)

Elevation of treatment-related lymphocytosis, particularly during the initial phase of treatment, will not be considered PD unless at least 1 other feature shows worsening (ie, lymphadenopathy, splenomegaly, anemia or thrombocytopenia meet criteria for disease progression) at the same evaluation or the next evaluation.

- Group B:
  - Platelet count decreases  $\geq 50\%$  from baseline secondary to CLL
  - Hemoglobin decrease of  $\geq 2$  g/dL from baseline secondary to CLL
  - Marrow shows increase of CLL cells by  $\geq 50\%$  on successive biopsies

Transformation to a more aggressive histology (Richter syndrome or Richter transformation) is also considered PD. The diagnosis of Richter transformation should be established by lymph node or other tissue biopsy.

**Stable Disease (SD):** if participant parameters do not meet criteria for PR, PD or CR

**Not evaluable (NE):** if any of the imaging, constitution and blood parameters cannot be assessed and criteria for PD are not met:

Note: Missing or inconclusive bone marrow data will not drive an assessment of NE by itself.

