#### 10.9.3.1 Overview

This appendix describes the process for assessing treatment response according to the IWWM Criteria for WM [Dimopoulos, M. A., et al 2014]. Assessments include:

- Imaging of abnormal lymph nodes
- Imaging of spleen and liver
- Measurements of serum IgM
- Detection of IgM by immunofixation
- Measurements of cryoglobulins
- Bone marrow biopsy
- Constitutional symptoms

- Plasmapheresis
- Amyloid (if applicable)

At baseline/screening, the participant should be assessed for the presence of extramedullary disease. If extramedullary disease is present, imaging should be used to assess the disease at baseline and follow-up timepoints. If there is no extramedullary disease at screening/baseline, then imaging does not need to be repeated at subsequent follow-up timepoints, unless clinically indicated.

Anatomic imaging may include CT, MRI or some combination of the 2. CT is the most common modality used, and for the purposes of this document the term “CT” will be used to represent all anatomic imaging, no matter which imaging modality is used.

Before treatment (“baseline”), if extramedullary disease is present on CT, all malignant lymph nodes (“nodal lesions”) will be classified as “target” (selected for quantitative assessment) or as “non-target” (selected for qualitative assessment). All focal non-nodal lesions are followed as non-target. The spleen will be assessed quantitatively (by measuring the craniocaudal length). If biopsy is performed, or if there are any physical examination findings that cannot be evaluated by imaging, these should be documented.

After therapy has begun, target lesions, non-target lesions, and the presence of new lesions in images will be assessed to provide a collective response in focal lesions (usually referred to as the “lymph node response” because the great majority of the focal lesions are lymph nodes). The spleen size will be assessed separately from focal lesions for an organomegaly response. Imaging responses (when applicable) are combined with changes in the clinical data (including serum IgM, immunofixation, cryoglobulinemia, bone marrow, constitutional symptoms, plasmapheresis, and amyloidosis) to produce an overall response at each timepoint.

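### The protocol contradicts itself on whether blood counts and serum IgM are assessed in Efficacy Follow-up, so progression shown only by them could be missed or dated late

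*Combined protocol and SAP*

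**What the plan says.** Two sets of passages govern participants who stop nemtabrutinib without progression.

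**Passages that name imaging only, or stop the tests**
- Section 8.11.5: "Participants who discontinue study intervention for reasons other than PD should continue with imaging assessments per the protocol-defined schedule until" progression, new anticancer therapy, death, withdrawal, pregnancy or study end.
- Section 8.2.2.1.1, for the same participants: "every effort should be made to continue monitoring disease status by tumor imaging using the same imaging schedule used while on treatment".
- SoA (Section 1.3.1): the row "Hematology, Serum Chemistry" is marked through Safety Follow-up and blank under Efficacy Follow-up. Physical Examination has the same pattern, and its note speaks of cycles: "For subsequent cycles, a directed physical examination will be performed". Serum Immunoglobulin is marked at Screening, C1D1, C2, C3, C4–C27 and C28+ and nowhere after. Its whole note is "For IgG, IgA, and IgM".

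**Passages that require the full assessment**
- Section 8.2 lists imaging, examination, symptoms, "hematological evaluations, and bone marrow as required) are required every 12 weeks", counted by calendar day from C1D1. The interval may widen to 24 weeks from the fourth year.
- Section 8.2.1.1 includes CBC and physical examination for CLL/SLL. Section 8.2.1.3 includes serum IgM and immunofixation for WM/LPL.
- Section 8.2.2 continues response assessments as well as imaging until progression, new therapy, withdrawal, death, pregnancy or study end. End of treatment is not on that list.
- Section 4.1 describes post-treatment follow-up of disease status, with imaging as one part.
- Appendix 9 calls for symptoms and blood counts (10.9.1.2.2) and serum IgM (10.9.3.2.2) at each follow-up timepoint.

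**The concern.** Progression is not purely an imaging event in two of the three disease groups. In CLL/SLL, Appendix 9 (10.9.1.3) lets lymphocytes, platelets or hemoglobin establish progression. It also makes a timepoint not evaluable "if any of the imaging, constitution and blood parameters cannot be assessed and criteria for PD are not met". In WM/LPL, a confirmed rise in serum IgM can establish progression alone, and a timepoint without IgM is not evaluable (10.9.3.3). For WM/LPL with no extramedullary disease at baseline, Section 10.9.3.1 adds "then imaging does not need to be repeated at subsequent follow-up timepoints, unless clinically indicated".

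If the tests are not done after treatment stops, a progression that only they would show is missed, or is recorded late when a scan or death reveals it. Both errors lengthen DOR, a secondary endpoint, and PFS, an exploratory one. The participants exposed are those who stop for a reason other than progression, such as an adverse event, and who must be followed off drug for the endpoint to be complete. The Lugano group is much less affected because its follow-up rests mainly on imaging.

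**Working it through.** The plan states no figure to reproduce. The check is a comparison of passages, followed by a rough count for scale.

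**1. SoA marks, over 13 visit columns**

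| Row | Columns marked | EOT | Safety FU | Efficacy FU |
|---|---|---|---|---|
| Physical Examination | 11 | X | X | blank |
| Hematology, chemistry | 11 | X | X | blank |
| Serum Immunoglobulin | 6 | blank | blank | blank |
| Treatment Response Assessments | 1 (Screening) | blank | blank | blank; timing in note |
| Cryoglobulins (WM/LPL) | 1 (Screening) | blank | blank | blank; timing in note |

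**2. What a blank cell means.** In the last two rows a blank cannot mean that the item is unscheduled, because imaging would then not be scheduled on treatment either. Their notes set the timing: every 12 weeks from C1D1 for response assessments, and each response assessment visit for cryoglobulins. The immunoglobulin row is different. It lists particular visits and its note gives no timing rule. The hematology and examination rows also list particular visits, and their notes set no timing for Efficacy Follow-up.

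**3. Which text a site would follow.** Three passages point to the SoA. Section 7.1 has participants who stop treatment complete the procedures that the SoA outlines. Section 8.3.6 has protocol-required laboratory tests done in accordance with the SoA. Appendix 2 has serum immunoglobulin collected as the SoA indicates. Sections 8.2 to 8.2.2 and Appendix 9 point the other way. A site could omit post-treatment IgM and cite the protocol, and another could draw it and also cite the protocol.

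**4. Where the gap bites.**
- WM/LPL without extramedullary disease: under the literal SoA and Section 8.11.5 reading, neither IgM nor a repeat scan is scheduled. Cryoglobulins remain tied to response visits, but they are not a listed progression criterion.
- CLL/SLL: imaging continues, so only progression by counts is exposed.
- Physical examination matters less in WM/LPL, since enlargement found by examination alone cannot drive progression there without other support (10.9.3.3).

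**5. Scale (assumption: the BELLWAVE-001 pattern in Section 2.2.2.3 carries over).** Planned enrolment is 6 to 12.
- Stopped for an adverse event: 28/136 = 0.206. Then 6 × 28/136 = 1.2 and 12 × 28/136 = 2.5 participants.
- Stopped for anything other than clinical or radiological progression: 23.5% and 19.1% of 136 are 32 and 26, so 107 − 32 − 26 = 49, and 49/136 = 0.360. Then 6 × 49/136 = 2.2 and 12 × 49/136 = 4.3. This overstates entry to Efficacy Follow-up, because it may include deaths and withdrawals.

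Both counts cover all diseases. The plan does not fix the disease mix, so the number with CLL/SLL or WM/LPL could be smaller, and for WM/LPL it could be zero.

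**The case against.** The strongest reply is that the tests are already required. Sections 8.2, 8.2.1.1 and 8.2.1.3 define the response assessment to include them, Section 8.2.2 carries it on until progression, and Appendix 9 repeats them for each follow-up timepoint. Section 8.2.2.1.1 is headed as an imaging section, and Section 8.2.2.1.2 deals with progression by laboratory findings. The note closing Section 8.11.5 speaks of efficacy assessments continuing on schedule, which can be read as the whole of Section 8.2.

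Most of this stands, and it rules out three stronger readings.
- A reader might infer that DOR and PFS cannot be determined after treatment stops. They can: the general text requires the measurements, and imaging progression and death would be captured in any case.
- A reader might infer that every Efficacy Follow-up timepoint is not evaluable for WM/LPL without extramedullary disease. That assumes IgM is never drawn, which Section 8.2.1.3 and Appendix 9 contradict.
- A reader might infer that, on treatment, cycle-based laboratory draws drift away from calendar-based response assessments after a dose hold. Counts and IgM are themselves components of the calendar-based assessment, so the text does not support this.

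The reply does not remove the contradiction. The immunoglobulin row gives explicit visits that end before EOT, three passages send sites to the SoA, and the operative sentence of Section 8.11.5 names imaging alone.

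**Conclusion.** The concern holds as an internal contradiction about the content of Efficacy Follow-up. It is not a complete absence of the assessments. If sites act on the SoA rows and Section 8.11.5, progression by IgM or blood counts can be missed or dated late, and DOR and PFS would be biased upward. WM/LPL without extramedullary disease is the most exposed group.

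The size of the bias cannot be given. It depends on how sites read the text, on the disease mix, and on rules for missing assessments, which Section 9.6.2 leaves to the supplemental SAP for DOR. If the 20.6% rate applies, about 1.2 to 2.5 participants would stop for an adverse event, and only some of them would be CLL/SLL or WM/LPL responders. Because DOR is computed in responders only, one misdated progression could still be visible in the summary.

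The stakes are modest: no hypothesis is tested, DOR is descriptive and reported only if there are enough responders, and PFS is exploratory. The correction is still worthwhile because it is specific and cheap.

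**What to change.** Reconcile the passages so that they give one instruction.

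1. In Section 8.11.5, replace the reference to imaging with *the full disease-specific response assessment per Section 8.2.1*.
2. Align Section 8.2.2.1.1 for participants who stop without progression, for example by a cross-reference to the revised Section 8.11.5.
3. In the SoA notes, tie serum IgM (WM/LPL) and CBC with differential (CLL/SLL) to each response assessment visit, including Efficacy Follow-up. The cryoglobulin row already uses this device.

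The cost is a wording amendment and a routine blood draw at visits already scheduled every 12 weeks, in the few participants who reach Efficacy Follow-up.
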